### 3.4 Summary of FARAPULSE Clinical Studies

#### 3.4.1 FARAPULSE Endocardial Ablation Clinical Studies

##### FARAPULSE IMPULSE Clinical Study

FARAPULSE, Inc, has initiated a safety and feasibility study at Na Homolce Hospital in Prague, Czech Republic and Hopital cardiologique du Haut-Leveque in Pessac, France under the “IMPULSE” Protocol, CS0188. This study is being conducted using the FARAPULSE Endocardial Ablation System; the same system which will be used in the subject investigation. Thirty-eight (38) patients have been enrolled between January and November of 2018. All patients were discharged in good condition. One patient was treated for tamponade at the conclusion of the index procedure. The event was resolved. One patient was treated for a supraventricular tachycardia seven months post procedure. The event was resolved. One patient underwent extended hospitalization for an early AF recurrence one day

post procedure. The event was resolved. At the conclusion of the index procedure all (100%) pulmonary veins (PVs) were isolated using the FARAPULSE device. Twenty-four (24) patients have returned for the protocol-defined 3-month remapping procedure to assess chronic PV isolation. Among these patients, 61% of PVs remained isolated at the 3-month remapping procedure. All PVs in eight (8) patients remained isolated. These results support both the safety and performance of the system.

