## 5.3 Study Endpoints

### 5.3.1 Primary Safety Endpoint

The primary safety endpoint for this study is the Composite Safety Endpoint (CSE) defined as the incidence of the following early-onset and late-onset serious adverse events (SAEs) which are device- or procedure-related:

Early onset (within 30 days of any endocardial ablation for atrial fibrillation)

- Death
- Myocardial infarction (MI)
- Persistent diaphragmatic paralysis
- Stroke or transient ischemic attack (TIA)
- Peripheral or organ thromboembolism
- Pericarditis
- Cardiac tamponade / perforation
- Vascular access complications
- Hospitalization (initial or prolonged)\*
- Heart block

Late onset (any time during follow-up)

- Pulmonary vein (PV) stenosis (> 70% diameter reduction from baseline)
- Atrio-esophageal fistula

\* Excludes hospitalization (initial & prolonged) solely due to arrhythmia (AF/Atrial Flutter/Atrial Tachycardia) recurrence or due to non-urgent cardioversion (pharmacological or electrical). Hospitalization excludes visits to hospital-associated outpatient facilities such as clinics or emergency wards.

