#### **5.12.5 75 Day Follow-Up**

Subjects will return for an office visit at 75 days ( $\pm$  15 days) post index ablation. At a minimum, the following data will be collected at the 75-day follow-up visit:

- Medications including use, changes in or discontinuation of anticoagulation, rate control and/or antiarrhythmic medications
- Pregnancy test (if applicable)
- Cardiac rhythm as determined by a 12-lead ECG
- Cardiac CT or MRI scan to assess the patency of the pulmonary veins
- 3D electroanatomical remapping procedure to assess electrical isolation of the pulmonary veins. Any electrical gaps may be closed at the investigator's discretion using a commercially approved ablation device. This will consist of placement of catheters in the left atrium via femoral access and transseptal puncture using conventional electrophysiology techniques. Any electrical gaps may be closed at the investigator's discretion using the study device or, if clinically necessary, using a commercially approved ablation device (which constitutes a therapeutic treatment failure).

- An Event Monitor will be provided to be used up to the 12-month follow-up visit for weekly scheduled and ad hoc symptomatic monitoring. Subjects will retain this device through the 12-month follow-up, ECG data from this monitor will be analyzed by a contract core lab. Investigational sites will be provided with the Event Monitor device and instructions for its use by the contract core lab. The investigational sites will then provide the device and instructions for use to the subject. The Event Monitor will be returned at the end of the subject's follow-up using shipping materials provided by the core lab.
- Cardioversions since last visit
- Heart failure status as assessed by NYHA classification at the time of visit
- Fluoroscopic Examination of Diaphragm Motion if the procedural examination indicates diminished phrenic nerve response
- Anticoagulation Monitoring: For subjects on anticoagulants, assessment of INR/PTT therapeutic levels as applicable/required (maintain as clinically indicated)
- Any additional ablation procedures performed
- Any hospital readmissions, including admission and discharge dates, since the previous visit
- Adverse Events

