#### **5.12.6 90-Day Phone Call**

In case the 75-day follow-up visit and electroanatomical re-mapping procedure occur earlier than planned, the subject will be contacted by phone to collect information on any hospitalizations, repeat ablations, adverse events and/or symptoms of AF, AFL, or AT at 90 days post index procedure.

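### The primary safety window opens only after an ablation, so a complication of the required 75-day remap counts if a gap is ablated and not otherwise; the rate then depends on lesion durability and operator choice

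*Combined protocol and SAP*

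**What the plan says.** Section 5.3.1 defines the CSE as listed "serious adverse events (SAEs) which are device- or procedure-related". Ten components fall under "Early onset (within 30 days of any endocardial ablation for atrial fibrillation". Only pulmonary vein stenosis and atrio-esophageal fistula fall under "Late onset (any time during follow-up". The synopsis and Section 7.6.1 repeat this, and no section names a mapping procedure as something that opens the window.

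Section 5.12.5 includes in the minimum data for the 75-day visit a "3D electroanatomical remapping procedure to assess electrical isolation of the pulmonary veins", done by "placement of catheters in the left atrium via femoral access and transseptal puncture using conventional electrophysiology techniques". The visit window is 75 ± 15 days (Section 5.12.5 and Table 4). Closing a gap is left to the investigator. The same paragraph first allows only a commercial device for this, and then the study device or, if clinically necessary, a commercial one.

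Table 3 defines cardiac tamponade/perforation by the 30 days after the index AF ablation, not after any ablation.

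Three other provisions matter. Secondary safety endpoint 1 (Sections 5.3.2 and 7.6.2) counts subjects with device- or procedure-related SAEs through 12 months, and endpoint 2 counts stroke or TIA through 12 months; neither is tied to an ablation. Section 10.10 has the Clinical Events Committee (CEC) adjudicate all procedure-related and serious events. Section 7.1 rules out hypothesis testing, and Section 7.2 says that the event rates and their confidence intervals will inform clinical dosage and the powering of a later study.

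**The concern.** The remap is a second femoral and transseptal procedure that the protocol itself requires. Whether its complications reach the primary safety endpoint depends on something other than harm: whether a gap was found and whether the operator chose to close it. Two subjects with the same access complication at the same remap are classified differently if one was ablated and the other was not. If a commercial catheter closes the gap, its procedure-related complications also enter the study system's composite, because the anchor is any AF ablation and procedure-relatedness is enough.

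The reported rate therefore rises as durability falls, even with the same risk at every procedure. Ablation dose is selected by the investigator (Section 5.12.2) and two catheter sizes are in use (Section 4.4.1). If a setting or size gave less durable lesions, more of its remaps would open a counted window, and a comparison of the CSE across settings would mix durability with safety. The same mixture would be carried into the planning of the next study.

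**Working it through.** The plan gives no derived figure to reproduce: the sample size is up to 80 with no formula, and no expected CSE rate is stated.

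**Step 1: windows.**
- Index window: day 0 to 30.
- Remap: 75 − 15 = day 60 to 75 + 15 = day 90.
- The earliest remap is 60 − 30 = 30 days after the index window closes. Unless a re-ablation in between has opened another window, an early-onset complication of a remap without ablation cannot be a CSE event.

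**Step 2: is a remap event procedure-related?** Section 5.3.1 does not define procedure. Section 8.1 asks for causality in relation to the device or any other study-related procedures, which favors including the remap. Relatedness would then be met in both cases, and the time window is what separates them.

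**Step 3: how many remaps fall on each side.** In IMPULSE, with the same system, 24 patients were remapped and "All PVs in eight (8) patients remained isolated" (Section 3.4.1).
- Durable: 8/24 = 33.3%, exact 95% CI 15.6% to 55.3%. With a gap: 16/24 = 66.7%.
- For 80 subjects, all remapped and all gaps closed: 80 × 0.667 = 53.3 inside the window and 26.7 outside. Over the CI for durability, 12.5 to 44.3 fall outside.
- If only half of the gaps are closed: 26.7 inside and 53.3 outside.

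**Step 4: effect on the CSE.** Let p be the complication risk per procedure (assumed; the documents give none for the remap), taken as equal for index, remap and re-ablation, and let g be the proportion re-ablated. The counted rate per subject is 1 − (1 − p)(1 − gp). Uncounted events are 26.7 × p.

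| p (assumed) | g = 0 | g = 0.667 | g = 1 | Uncounted events at g = 0.667 |
|---|---|---|---|---|
| 1% | 1.0% | 1.7% | 2.0% | 0.27 |
| 2% | 2.0% | 3.3% | 4.0% | 0.53 |
| 4% | 4.0% | 6.6% | 7.8% | 1.07 |

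For example, at p = 2% and g = 0.667: 1 − 0.98 × (1 − 0.0133) = 3.3%. The expected counted events are 80 × 0.02 = 1.6 from index procedures and 53.3 × 0.02 = 1.07 from second procedures, so 1.07/2.67 = 40% of counted events come from the second procedure. The chance of at least one uncounted event among 27 subjects is 1 − 0.98^27 = 42%.

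**Step 5: the same check with separate index and remap risks.** Take the index risk as 1/38 = 2.63% (the one tamponade listed for IMPULSE, for illustration only) and the remap risk as 2%. The counted CSE is 2.63% if all subjects are durable, 3.93% if one third are, and 4.58% if none are. If every left-atrial procedure opened the window, it would be 4.58% at any durability.

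**Step 6: follow-up of the second window.** It closes 30 days after the re-ablation. The 90 ± 7 contact falls on days 83 to 97, so it can reach the end of the window only for remaps up to day 97 − 30 = 67. A day-75 re-ablation has a window to day 105, and the next visit is at day 150 to 210.

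**The case against.** The strongest reply is that the study's objective concerns PEF ablation, so tying the window to ablation is defensible, and that the size is small. At an assumed 2%, 3.3% is counted where 4.0% would be if every procedure counted; the difference is about half of one subject, since one subject of 80 is 1.25 points. The risks are assumed, equal risk for diagnostic mapping and ablation is assumed, and closing every gap is assumed although it is discretionary. None of the events listed for IMPULSE is attributed to a remap, although 24 patients had one. All of this stands and limits the severity. It does not remove the point: 0 of 24 is compatible with a risk up to 1 − 0.025^(1/24) = 14.2%, and an endpoint about ablation would not include commercial-catheter harm in the study system's figure without labeling it.

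A reader might infer three stronger things that the documents do not support.

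- **That remap complications are lost from the study.** They are not. Secondary safety endpoints 1 and 2 and CEC adjudication still cover them, and Table 4 collects adverse events through 12 months. (Section 8.2 speaks of monitoring through discharge, which needs its own reconciliation with Table 4.)
- **That a remap tamponade counts when a gap is ablated.** Section 5.3.1 says so, but Table 3 limits this component to the index procedure. Read literally, Table 3 excludes it whether or not ablation takes place. The two contradict each other, so stroke, embolism and access complications are the clean examples.
- **That the 90-day call always comes too early.** "In case the 75-day follow-up visit and electroanatomical re-mapping procedure occur earlier than planned, the subject will be contacted by phone", so the subjects called are those remapped early. For remaps on days 60 to 67 the call can fall at or after the close of the window.

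**Conclusion.** The point holds as a should-fix. The direction follows from the text and timing alone: with equal harm, more re-ablation gives a higher CSE. The size rests on the assumed risks and on 24 IMPULSE patients. At 2% per procedure the CSE moves between 2.0% and 4.0% across the full range of re-ablation, with about 0.5 events in 80 uncounted at IMPULSE durability. The late-onset components are unaffected.

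It would be tempting to say that this undermines a safety conclusion. The plan has no test, performance goal or comparator, so no decision rule is affected. What suffers is the interpretation of a descriptive rate and its use in planning. The contradiction between Section 5.3.1 and Table 3 on tamponade stands whatever risks are assumed.

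**What to change.** 1. In the synopsis, Sections 5.3.1 and 7.6.1, and Table 3, state consistently that the early-onset window covers 30 days after the index ablation, after the 75-day remap with or without ablation, and after any other endocardial ablation for AF. Reconcile the Table 3 tamponade wording with this, and say that procedure-related includes the remap.
2. Attribute each CSE event to one procedure: index study-device ablation, remap only, study-device re-ablation, or non-study-device re-ablation. Report the total and each line. The study-device figure should be index plus study-device re-ablation; the index line alone would leave out re-ablations with the study device, which Section 5.12.5 permits. The two statements there about which device may close a gap need to be reconciled.
3. Optional: reconcile the 90-day contact, which is listed for all subjects in the synopsis and Sections 5.1 and 5.6 but is conditional in Section 5.12.6 and Table 4. Whatever is settled, ask explicitly about events in the second 30-day window, at the latest at the 6-month visit.

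The cost is wording in four places, one CRF field and four table lines. For subjects already enrolled, the attribution can be made from procedure and event dates. The downside is a total composite that may be slightly higher and that includes diagnostic-procedure risk; the separate lines make that visible. The change should be made before the CSE is tabulated.

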Ablation treatment paradigms have evolved over time, and current strategies emphasize isolation of the pulmonary veins (PVI) as the cornerstone of catheter ablation of AF. Energy sources for endocardial lesion creation have included radiofrequency, cryo (freezing), laser, ultrasound and microwave. New ablation techniques and devices continue to develop with the objective of improving safety and efficacy, while reducing procedure time (complexity). In elite single-center reports, the success rate for eliminating symptomatic AF (inclusive of both PAF and continuous AF subjects) varies from 55% - 77%, with many patients requiring multiple procedures. Retreatment rates as high as 40% have been reported.

Understanding the need for creating electrical isolation of the pulmonary veins, treatment paradigms have focused on creating circumferential lesions or wide circumferential lesion sets that block electrical continuity between the pulmonary veins and the left atrium. In a wide circumferential ablation (WACA) procedure, operators must form a contiguous line of electrical block around ipsilateral pulmonary veins using fluoroscopic guidance and electroanatomical mapping technologies. A limited assessment of lesion formation and position is determined by monitoring voltage reduction of the local electrogram at the target site. Electrical gaps in lesion sets occur frequently, leading to recurrent AF and/or creation of substrate susceptible to reentrant atrial tachycardias. Ablation technologies that rely upon indirect assessment of lesion formation are challenged to deliver improved durability and therefore long-term efficacy of therapy.

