**Table 3. Primary AE Safety Endpoint Definitions**

Primary Adverse Event	Description/Criteria
Death	Death
Myocardial infarction (MI)	Myocardial infarction will be demonstrated by any one of the following: 1) detection of ECG changes indicative of new ischemia (new ST-T wave changes or new LBB) that persist for more than 1 hour. 2) development of new pathological Q waves on an ECG 3) imaging evidence of new loss of viable myocardium or new regional wall motion abnormality
Persistent diaphragmatic paralysis	Change in baseline diaphragmatic function as evidenced by elevation of the diaphragm above the normal range but not due to a pulmonary process such as atelectasis.
Stroke or transient ischemic attack (TIA)	Stroke is an acute symptomatic episode of neurological dysfunction attributed to a vascular cause (ischemia or hemorrhage) in which symptoms last more than 24 hours, or if symptoms last less than 24 hours, a brain imaging study demonstrates infarction.  Transient ischemic attack is a new focal neurological deficit with rapid symptom resolution always within 24 hours.
Peripheral or organ thromboembolism	Formation in a blood vessel of a clot (thrombus) that results from the breaking loose of all or part of an existing thrombus, which is then carried by the blood to lodge in/occlude a more distal vascular site.
Pericarditis	Inflammation of the pericardial space that results in an effusion that leads to hemodynamic compromise or required pericardiocentesis, prolongs hospitalization by more than 48 hours, requires hospitalization, or persists for more than 30 days following the ablation procedure.
Cardiac tamponade/perforation	The development of a significant pericardial effusion during or within 30 days of undergoing the index AF ablation procedure. A significant pericardial effusion is one which results in hemodynamic compromised (<80mmHg systolic bp), requires elective or urgent pericardiocentesis, or results in a 1cm or more pericardial effusion as documented by echocardiography.
Vascular access complications	Vascular access complication (e.g. groin hematoma, AV fistula, pseudoaneurysm) requiring intervention (e.g. surgical repair, blood transfusion) or admission or prolonged hospitalization.
Hospitalization (initial or prolonged)	*excludes hospitalization (initial or prolonged) solely due to arrhythmia (AF/AFL/AT) recurrence

Primary Adverse Event	Description/Criteria
	or due to non-urgent cardioversion (pharmacological or electrical)

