### 5.3.4 Secondary Feasibility Endpoint

1. The proportion of subjects that achieve Chronic Procedural Success (CPS) defined as persistent electrical isolation of all initially ablated pulmonary veins assessed during an electroanatomical mapping procedure performed 75 days following the index procedure. Chronic Procedural Success will be subdivided by single procedure and reablated subjects.
2. The proportion of subjects that achieve Therapeutic Success, defined as freedom from:
  - a. Post blanking period through assessment: occurrence of AF, AFL or AT, or ablation for AF/AFL/AT using the study device
  - b. At any time: ablation for AF/AFL/AT with a nonstudy device

Therapeutic success will be assessed from the end of the blanking period at Months 6 and 12, and will be subdivided by on / off AFDs post blanking period.

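### The 30-day primary safety window omits study-device re-ablation done solely for flutter or atrial tachycardia, and Table 3 narrows tamponade further, to the index procedure

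*Combined protocol and SAP*

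**What the plan says.** The CSE counts "serious adverse events (SAEs) which are device- or procedure-related". Its twelve components fall into two groups. Ten are headed "Early onset (within 30 days of any endocardial ablation for atrial fibrillation"; the other two, pulmonary vein stenosis and atrio-esophageal fistula, are headed "Late onset (any time during follow-up". The Executive Summary and section 7.6.1 repeat this wording.

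Therapeutic Success (section 5.3.4, repeated in the Executive Summary and 7.5.2) describes retreatment more widely. After the blanking period it requires freedom from "occurrence of AF, AFL or AT, or ablation for AF/AFL/AT using the study device". A second criterion reads "At any time: ablation for AF/AFL/AT with a nonstudy device".

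Table 3, which defines the CSE components, dates cardiac tamponade/perforation as arising "during or within 30 days of undergoing the index AF ablation procedure". No other row of the table is tied to the index procedure.

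For the 75-day remap, section 5.12.5 states: "Any electrical gaps may be closed at the investigator's discretion using the study device", with a commercial device as the alternative.

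**The concern.** The composite's own test is whether a serious event is related to the device or the procedure. The heading of the early-onset group adds a second test, the arrhythmia for which the ablation was done. If the study catheter is used again solely for AFL or AT after earlier windows have closed, no new window opens. A related stroke or vascular access complication of that procedure then stays out of the primary rate, although it would count had the recorded indication been AF.

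The effect runs one way. A narrower trigger can only remove events, and it does so in subjects who needed a second procedure. Section 7.2 says that the event rates and confidence intervals from this study will inform the powering of a later pilot study, so the definition of the numerator has a use beyond this report.

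Table 3 adds an open contradiction. For tamponade/perforation, one of the more serious acute components, section 5.3.1 includes re-ablations for AF and Table 3 does not.

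**Working it through.** **Plan's own figure.** There is none to reproduce. Section 7.1 states that there is no hypothesis test and no required sample size, and no CSE rate is assumed. The check is therefore a comparison of wording, followed by a size estimate.

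**Step 1: which procedures open the early-onset window.**

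| Procedure | Window under 5.3.1 | Tamponade row of Table 3 |
|---|---|---|
| Index isolation, with or without cavo-tricuspid isthmus ablation | open | counted |
| Pulmonary vein gap closure at the 75-day remap (repeat isolation for AF) | open | not counted |
| Later re-ablation for AF, alone or combined with AFL/AT | open | not counted |
| Study-device re-ablation solely for AFL/AT, more than 30 days after the last AF ablation | not open | not counted |

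Pulmonary vein stenosis and atrio-esophageal fistula count after all four. The literal gap in 5.3.1 is the last row, for ten of twelve components. The contradiction with Table 3 covers rows two and three, for one component.

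**Step 2: timing.** The index window closes at day 30 and blanking ends at day 90. The remap is at 75 ± 15 days, so a window opened by gap closure there closes at day 90 + 30 = 120 at the latest. Follow-up runs to 12 months. From day 120 on, an AFL/AT-only re-ablation falls in a window only if there has been a further AF ablation in the preceding 30 days.

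**Step 3: size of one omission.** Assume all 80 subjects are treated and the omitted subject has no other CSE event. The change is 1/80 = 1.25 percentage points. Exact (Clopper-Pearson) 95% limits:

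- 0/80: upper limit 1 − 0.025^(1/80) = 4.5%
- 1/80 = 1.25%: 0.03% to 6.8%
- 2/80 = 2.5%: 0.3% to 8.7%

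**Step 4: how often.** The number of AFL/AT-only re-ablations is m = 80 × recurrence × AFL/AT share. The chance of at least one omission is 1 − (1 − c)^m, with c the complication rate per re-ablation.

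- Recurrence 20% to 40%: the literature range in section 3.5.
- AFL/AT share 10% to 50%: assumed, not in the documents.
- c of 2% to 10%: assumed.
- Every recurrence re-ablated with the study device, outside any open window: assumed, and generous.

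Low end: m = 80 × 0.20 × 0.10 = 1.6; expected omissions 1.6 × 0.02 = 0.03; chance of at least one 1 − 0.98^1.6 = 3%.

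High end: m = 80 × 0.40 × 0.50 = 16; expected omissions 16 × 0.10 = 1.6; chance 1 − 0.90^16 = 82%.

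With c = 3.2%, the catheter-arm adverse event rate that section 3.2 quotes from another trial, the same two values of m give 1 − 0.968^1.6 = 5% and 1 − 0.968^16 = 41%.

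A cross-check closer to the device: section 3.4.1 reports one supraventricular tachycardia treated among 38 IMPULSE patients. If that treatment was an ablation, which is not stated, 80 × 1/38 = 2.1 procedures, 2.1 × 0.032 = 0.07 expected omissions and a chance of about 7%. Follow-up there was incomplete.

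**The case against.** Much of the case on the other side stands.

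- **The set is narrow.** The only re-ablation that the protocol schedules an occasion for is gap closure at the remap, and that is repeat vein isolation in an AF study. Isthmus ablation for flutter is planned within the index procedure. A reader might infer that all complications of re-ablation are left out; the wording of 5.3.1 does not support that.
- **AFL/AT re-ablation is foreseen, not forecast.** Section 3.1 speaks of lesion gaps "leading to recurrent AF and/or creation of substrate susceptible to reentrant atrial tachycardias", but as background after describing wide circumferential ablation. The arrhythmia list in the CSE footnote concerns hospitalization, not ablation. Therapeutic Success shows that such procedures are possible, no more.
- **The exclusion is never stated.** The device's intended use is paroxysmal AF (section 4.2), so the Clinical Events Committee could read ablation for AF as any study ablation. That would close the gap in practice. It also means that the primary endpoint can be read two ways, and it should be settled before adjudication.
- **The events are not lost.** Secondary safety endpoint 1 counts every subject with a related serious event through 12 months, and the committee adjudicates all procedure-related and serious events. Neither corrects the primary rate.
- **Tamponade is a poor example of dependence on indication.** A reader might infer that tamponade at re-ablation counts when the indication is AF. Under Table 3 it does not, whatever the indication. It could still enter through the hospitalization component if the stay is prolonged after an AF re-ablation, which softens the conflict without removing it.

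**Conclusion.** The point holds in a limited form. Read literally, the ten early-onset components are not counted after a study-device re-ablation done solely for AFL or AT more than 30 days after the last AF ablation, and no other section repairs this. Separately, Table 3 contradicts 5.3.1 on tamponade/perforation after any re-ablation; that conflict is wrong as written.

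Each omitted subject lowers the CSE by 1.25 points at n = 80. The number of omissions cannot be fixed from the documents: the range of 3% to 82% for at least one rests on assumed shares and rates and on the generous premise that every such repeat goes uncounted, so its upper end is a ceiling. A reader might infer a material downward bias in the reported safety of the device. The documents do not support so strong a claim: they show a one-sided rule with a small reach, in a descriptive study where no alpha, power or decision threshold is affected. This is a cheap improvement to the endpoint definition, together with a correction to Table 3.

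**What to change.** In the Executive Summary and sections 5.3.1 and 7.6.1, define the early-onset window as within 30 days of any endocardial ablation for AF, or of any ablation for AF/AFL/AT using the study device. In the tamponade/perforation row of Table 3, replace the reference to the index AF ablation with that same window; changing only the three endpoint statements would leave the contradiction in place.

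Limiting the addition to study-device procedures matters. Opening the window after every AFL/AT ablation would bring complications of commercial-catheter flutter procedures into the safety rate of the study device.

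The cost is one phrase in three places and one table row. Additional ablations are already recorded at the 75-day, 6-month, 12-month and unscheduled visits, and Therapeutic Success already needs the device used, so no new data collection is required. The downside is that the CSE may become slightly less favourable.
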